7.6 Method of estimation

In the main, we will use OLS to generate our ITT and CATE estimates. For some variables such as medical expenditures, debt, and monthly expenditure budget, we will be interest not in the effect on the mean of outcome variables but on the distribution of the outcome or on tails. For those variables we will use quantile regressions or distribution regressions when the treatment variable is continuous, e.g., share of village sample in a given arm or set of arms (Chernozhukov et al. 2013). We will compare CDFs of outcome variables when we compare outcomes across two or more discrete groups.

8 Outcomes of interest

The following are outcome variables, organized into groups by subject, that we will examine. We shall indicate those which will be analyzed as part of an index.

In each group, we will also list coloring variables that shed light on mechanisms behind causal relationships, on dosage of treatment, or on the welfare implications of treatment. We describe how we use these controls in Sections 7.1 and 7.2. Note, in some cases, outcome variables also serve as coloring variables.

8.1 Demand for insurance

8.1.1 Uptake

- Take up RSBY at enrollment (in 2015)

¹⁴We will also consider multiple testing approaches as raised in Lee and Shaikh (2014).

- Possession of RSBY card at endline
- Possession of RSBY card in past
- No longer have RSBY card
- Number of household members on RSBY card

Coloring variables

- Date RSBY card acquired
- Why household no longer has RSBY card
- Expected RSBY card but did not receive it

8.2 Utilization

The following were asked separately for a sickness (as screened using the same criteria as our PHES instrument) and the most serious treated case (defined as largest expense or longest length of stay).

- Seek treatment for an illness (with illness defined by PHES screens)
- Visit a clinic
- Visit a hospital
- Visit a private (versus government) hospital
- Length of stay
- Any medical expenses

The following outcomes were measured on all subjects

- Had a day surgery
- Number of day surgeries
- Type of day surgery
- Tried to use RSBY card
- Were able to use RSBY card
- How many times did you visit a hospital?
- How many nights did people stay in a hospital across all hospital visits?
- Knowledge about RSBY (number correct out of 4 questions)
- Subjective willingness-to-pay for RSBY

Coloring variables for last 2 sets of outcome variables

- Did you have an illness (as defined by PHES screens)
- Number of household members on RSBY card
- Age (child or adult) and gender of household members on RSBY card
- Household has BPL card
- When RSBY stopped being valid
- Unable to use RSBY card
- Expected RSBY card but did not receive it
- Why household did not try to use RSBY card

- Why household was unable to use card
- Age (child or adult) and gender of person who was ill (with illness defined by PHES screens)
- Did RSBY card pay for day surgery
- Verified eligibility for NHPS (National Health Protection Scheme or Ayushman Bharat)
- Verified claims under NHPS

8.3 Financial value

8.3.1 Financing care

The following were asked for the most serious treated case (defined as largest expense or longest length of stay) and for all medical treatments.

- Total cost of treatment
- Total amount paid by RSBY card for treatment
- Total cost of treatment net of RSBY payments
- Total amount paid for care with money outside households (other than RSBY)
- Borrowed money to pay for treatment
- Amount borrowed to pay for treatment
- Borrowed money to pay lost income
- Amount borrowed to pay for lost income
- Interest rate (or duration to repay and amount repaid) on largest loan
- Total amount paid for care with money from within household
- Amount paid with own savings
- Sold assets in response to sickness
- Value of assets sold in response to sickness
- Household worked more to pay for treatment
- Canceled or delayed expense to pay for treatment

The following were asked only of all medical treatments

- Spending on health care, by provider (hospital, clinic, medication, traditional medication, tests, other)
- Medical expenses, variability
- How household would pay for medical expenses from a hypothetical hospitalization

Coloring variables for the last set of outcome variables

- Spending on health care, by provider (hospital, clinic, medication, traditional medication, tests, other)

Coloring variables for the last 2 sets of outcome variables

- Why household did not try to use RSBY card
- Why household was unable to use card
- Interest rate (or duration to repay and amount repaid) on largest loan

- Number of months permitted to repay largest loan
- Total amount borrowed on largest loan
- Total amount to be repaid on largest loan
- Expense canceled or delayed to pay for treatment was business (versus household) expense
- Asset that could be sold to raise Rs. 8000 in emergency: existence, purchase price, use for asset, earnings from asset, loss of earnings from sale of asset, earnings from urgent (versus non-urgent) sale)
- When, in last 5 years, was last item or service worth INR 8000 purchased? (If none, then item greater than INR 2000?) Surplus from that item (willingness to pay - amount paid)?

8.3.2 Consumption

- Monthly expenditure, typical month
- Monthly expenditure (net of medical expenses), typical month
- Monthly expenditure, variability
- Delay consumption

Note: To improve precision, we will estimate expenditure specifications in which we impose a household-level budget constraint, as in [Kaboski et al. \(2018\)](#).

8.3.3 Income

The following outcomes were measured on all subjects.

- Now have BPL card
- Missed 2 or more days of work or school (as defined in PHES)
- Earn money from a business
- Net business income, last month
- Net business income, variability
- Average daily income of ill person
- Business income, typical day
- Number of people working for household business (versus outside the business)
- Work outside household business: number of days and total income

Coloring variables for the last set of outcome variables

- Number of people working for household business (versus outside the business)
- Work outside household business: typical daily income

The following were asked separately for a sickness (as screened using the same criteria as our PHES instrument) and the most serious treated case (defined as largest expense or longest length of stay).

- Missed work due to sickness and any treatment
- Days of work lost due to sickness and any treatment
- Loss of income due to sickness and any treatment

Coloring variables

- Average daily income of ill person

8.3.4 Assets and investment

- Business asset: existence, change in amount, illiquidity, loss of value from quick sale
- Financial well-being, as measured on financial ladder and by reduction in consumption due to financial difficulty
- Own or rent home
- Rooms in home
- Number of pucca rooms, semi-pucca rooms
- Index¹⁵ of select business and non-business assets.
- Index¹⁶ of livestock
- Acres of land owned
- Cash (in savings accounts or other locations)

Coloring variables for the last set of outcome variables

- Nature of business
- Business asset: loss of value from quick sale

8.4 Health value

- Sickness (as defined in PHES)
- Pregnancy or stillbirth (as defined in PHES)
- Self-reported health rating (1 to 5)
- Mortality (all cause and sickness-associated)
- Weight

8.4.1 Chronic disease

- High blood pressure: diagnosed, treated
- Diabetes: diagnosed, treated (at all, insulin, special diet)
- Cancer: diagnosed, treated
- Chronic lung disease: diagnosed, treated
- Heart condition: diagnosed
- Stroke: diagnosed
- Arthritis or rheumatism: diagnosed, treated (arthritis)
- High cholesterol: diagnosed, treated
- Eyesight problems: diagnosed, treated

¹⁵We describe how we construct this index and what assets we include in the index in an appendix to this document.

¹⁶See prior footnote.

8.4.2 Infectious disease

- TB
- Malaria
- Dengue
- Chikungunya
- HIV/AIDS
- Chickenpox
- Typhoid
- Hepatitis
- Pneumonia
- Diarrheal diseases
- Influenza
- Jaundice

8.4.3 Health-related quality of life, ADLs, and physical health symptoms

- ADL index (as defined in PHES)
- SF-8 battery
- Types of pain (after being screened in for pain by SF-8)
- Physical health symptoms
 - Dizziness
 - Fainting
 - Shortness of breath
 - Feeling your heart pound or race

8.4.4 Mental and emotional health and cognitive function

- GHQ-12 (to measure depression)
- PSS-10 (to measure stress)

8.4.5 Health behaviors

- Smoking: existence, amount
- Drinking: existence, amount
- Physical activity: amount of moderate, amount of vigorous
- Composition of diet: frequency of cereals, pulses, milk, leafy vegetables, fruits, eggs/poultry/fish/meat, salty and fatty foods, soft drinks

8.4.6 Fertility

- Number of total births
- Number of live births
- Number of still births
- Location of births
- Who assisted during birth
- Complications during births
- Ideal fertility (midline)

8.4.7 Coloring variables

Because utilization and financial impacts are mechanisms through which insurance may affect health, the coloring variables in those sections may also serve as coloring variables for health outcomes.

8.5 General coloring variables

The following is a non-exhaustive list of variables that may be used as control variables that measure dosage, specific margins of response or dosage. This list is non-exhaustive as it lists only those variables measured at endline and not otherwise included as a coloring variable above.

- Gender of respondent
- Age of respondent
- Role of respondent in household (relationship to head of household)
- Size of household
- Number of adults in household
- Number of children in household
- Knowledge of BPL households and how many
- Knowledge of BPL households with RSBY cards and how many
- Knowledge of household that successfully used RSBY
- Knowledge about RSBY (number correct out of 4 questions)
- Knowledge of when RSBY scheme expired
- Subjective willingness-to-pay for RSBY
- Knowledge about NHPS
- Does respondent think household is covered by NHPS
- One item test of NHPS (does respondent know about amount of coverage)
- Did any other individuals assist with answering questions during the survey? If so, what is the gender and relationship to respondent? ¹⁷

¹⁷Additional respondents may affect the response quality in both positive and negative ways. For finance questions, these individuals may improve the precision of the responses. For health questions, these individuals may lead to decreased precision. Please note that enumerators were instructed to administer health questions without any additional individuals present to minimize this concern.

9 Structural modeling

We plan to develop an economic model of household financial decisions and health status. We will structurally estimate the model using the experimental variation, to quantitatively reconcile the rich set of empirical results and perform counterfactual analysis.

10 Why is higher price for insurance associated with higher utilization?

At midline we found that individuals in group C, which had to pay a premium for insurance but did not get an unconditional cash transfer, had higher rates of utilization of the RSBY card. We will explore three explanations. First, individuals that value insurance more because they are more likely to use it are more likely to take up insurance, i.e., there is selection. Second, a higher price for a good sends a positive signal about the quality of the good, and higher quality goods are consumed more. Third, there is some sunk cost effect.

We will test this finding again at endline, and we will test which of these explanations for the midline finding (and potential endline finding) have merit. Our specific analyses are listed below.

10.1 Higher price causes greater utilization

We test whether the midline finding persists at endline in two ways:

- We examine whether group C households have higher rates of attempts to use RSBY and successful efforts to use RSBY.
- Because households with more members have a lower effective price per member¹⁸, larger households should have greater utilization per capita (as opposed to per household).

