4.2.1 Access to RSBY

We evaluate three methods of accessing RSBY:

- A. Free RSBY. Households obtain access to RSBY for no charge, not even the INR typically charged to obtain a biometric, smart card that functions as the insurance card.
- B. Right to purchase RSBY and an unconditional cash transfer equal to the premium. Households obtain an unconditional cash transfer equal to the RSBY premium in their district plus the right to buy RSBY in the following 3 weeks.
- C. Right to purchase RSBY. Households receive the right to buy RSBY in the next 3 weeks, but no cash transfer, conditional or otherwise.

We compare outcomes under these conditions versus a control condition:

- D. No intervention.

We choose these interventions because they address important academic and policy questions. Programs such as RSBY in India or Medicaid in the US are actually two conceptually distinct interventions: access to insurance at full price (i.e., pure insurance) and a (conditional) cash transfer equal to the insurance premium. Moreover, different interventions have different budgetary effects; we want to net these out by comparing budget neutral alternatives such as conditional and unconditional cash transfers. We seek to value each of these interventions. These not only have different effects, they are different policy options available to the government. Comparing condition C to condition D yields the value of pure insurance. Comparing condition A to C yields the value of a conditional cash transfer. Finally, comparing conditions A and B yields the difference between a conditional and an unconditional cash transfer.

5 Evaluation Design

We carried out a randomized controlled trial (RCT) to test the impacts of the RSBY expansion to APL households.

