5.4 Treatment Delivery

The population that is eligible for this study would not be eligible for RSBY under the program's usual rules. To make this study possible, we exchanged letters of cooperation with the state in which we conducted the study (Karnataka), the central government agency (Ministry of Labor) responsible for administration of RSBY, and the development organization (GIZ) providing technical support for RSBY.

Sample households were randomized in August 2014 using data from the listing exercise. They were informed of their treatment assignment and, depending on which arm to which they are assigned, given access to insurance or cash in May and June 2015. This step took place roughly 18 months after the baseline due to government constraints. Due to challenges associated with evaluating a government program, we were only able to enroll sample households when the government held its RSBY enrollment drive in early 2015.

We enrolled study households much in the same way the government enrolled RSBY (non-study) eligible households into the program: via a mobile enrollment truck that visited each village. One difference is that we went to each household to ask them if they would like to enroll and took them to the enrollment truck, which was parked in one place in the village. By contrast, the government informed non-study households by delivering paper notices (chits) to each home about when and where the enrollment truck would be in the village.

Roughly 78.4%, 70.4% and 58.6% of households in arms A, B, and C, respectively enrolled in RSBY. Enrollment rates are somewhat higher in Gulbarga than Mysore: 77.9/76.4/64.1% v. 78.8/63.5/52.3% in A/B/C. No one in arm D enrolled.

For all study households that take up insurance, we paid the government their premiums. For households in arms A, this was funded by grant funds. For those in B and C that purchase insurance, this was funded by the respondents' money.

The Karnataka government renewed RSBY automatically for non-study and study households in 2016 and 2017 without any action—even payment—by enrollees. RSBY ended in the state on August 31, 2018, to make way for the new NHPS scheme, which is scheduled to start in late 2018 or early 2019. As of this writing, Karnataka had agreed to roll out NHPS but had not begun the roll-out.

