11. Age or child/adult status
12. Marital status, birth order and relationship to household head
13. Size of village
14. Percent of village assigned to access to RSBY via this RCT
15. Percent of village eligible for RSBY outside the RCT
16. Hospital utilization in prior year (measured at baseline) or predicted hospitalization
17. Health status or serious sickness
18. Cognitive capacity
19. Willingness to pay for insurance (predicted based on data from a randomly selected sample of households removed from main RCT and chosen to participate in a WTP study)
20. Risk and time preferences
21. Assets and savings
22. Urban, peri-urban, and rural status
23. Monthly expenditure budget
24. Experiencing a serious health shock in the past year (provided this is balanced across treatment arms)

Predicting utilization. A natural dimension along which the impact of insurance may differ is the latent propensity of a household to experience health shocks which would require inpatient care. Since this variable is latent, it must be estimated. We will machine learning methods to predict households' likelihood to experience an inpatient hospitalization. We will perform this exercise on two samples: the baseline data (across all treatment arms) and the post-intervention data (using only group D, the control group). The resulting model will then be used to generate predictions for the full sample. Our key hypotheses are (1) that the impact of the offer of insurance will lead to larger treatment effects for those with higher propensity; and (2) that demand for insurance will be less price-elastic among those with higher propensity (i.e., adverse selection). Hypothesis (2) will be tested by examining how takeup of insurance varies between free and not free (group A vs. groups B and C) for high- vs. low-propensity households.

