10.2 Selection

We test this explanation by testing its assumptions or predictions:

- Individuals who were differentially sick or risk averse at baseline are more likely to enroll in RSBY in the first place and/or retain the RSBY card at midline and endline, conditional on household group assignment.
- Total utilization should be weakly higher in household group A than C. Equivalently, average utilization including both enrollees and non-enrollees, i.e., the ITT estimates of utilization, should be higher in A.¹⁹
- After predicting those in group A likely to enroll if they were in group C, we test to see if they have higher utilization conditional on getting insurance.

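### Section 10.1 tests a price effect through group C, with no comparator and without arm B, so a difference that comes through cash could be reported as price or sunk cost

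*Combined protocol and SAP*

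**What the plan says.** Section 4.2.1 defines the arms. A receives RSBY free. For B, "Households obtain an unconditional cash transfer equal to the RSBY premium in their district plus the right to buy RSBY in the following 3 weeks". For C, "Households receive the right to buy RSBY in the next 3 weeks, but no cash transfer, conditional or otherwise". Section 5.4 confirms that purchasers in both arms bore the premium: "For those in B and C that purchase insurance, this was funded by" the purchasers themselves.

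Section 10 opens with the midline result to be explained: "individuals in group C, which had to pay a premium for insurance but did not get an unconditional cash transfer, had higher rates of utilization". What is being used here is the insurance card, and no comparison arm is stated. Section 10.1 re-tests this at endline: "We examine whether group C households have higher rates of attempts to use RSBY and successful efforts to use RSBY". Again no comparator is named. The arm contrast in section 10.2 is A with C: "Total utilization should be weakly higher in household group A than C". The explanations on offer are selection, price signaling and sunk costs. Section 10.4 specifies no test for sunk costs and counts failure of the other two in its favor. B enters no arm contrast in section 10, and income or liquidity is not listed.

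Hypothesis (2) in section 7.3 concerns whether demand is less price-elastic at high predicted propensity to be hospitalized. It is tested by "examining how takeup of insurance varies between free and not free (group A vs. groups B and C" pooled, compared between high- and low-propensity households.

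Elsewhere, section 4.2.1 names C v D, A v C and A v B as comparisons of interest, but not B v C. Section 3 asks about an income effect of premium subsidies (question 1(g)) separately from the effect of prices (question 2).

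**The concern.** The meaning of a high rate in C depends on the arm it is set against. Against B, the price is the same and only the cash differs. Against A, the price differs and neither arm receives cash. Against A and B together, the two are blended. Section 10.1 leaves the choice open under a heading that makes a causal claim about price.

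The residual rule in section 10.4 adds to the risk. B purchasers pay the same premium as C purchasers, so a C excess confined to the comparison with B is not evidence of a sunk-cost effect. With income and liquidity off the list, the plan has nowhere else to put it. At stake is the answer to question 2: a reader could conclude that charging a premium raises use, when the data show that withholding cash changed who enrolled or what they could afford.

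The treatment of B is also inconsistent. Section 10 sets C apart partly by its lack of cash, while section 7.3 groups B with C as not free.

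**Working it through.** **Arm sizes.** Table 1's village shares times household shares reproduce its totals. For A, (15×30 + 15×30 + 15×30 + 35×70 + 20×10)/100 = 40%. B, C and D each come to 20%. Applied to the 11,089 randomized households, this gives about 4,436 in A and 2,218 in each of B and C.

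**What each contrast changes (section 4.2.1).**

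| Contrast | Premium | Unconditional cash |
|---|---|---|
| A v B | changes | given in B, roughly offsetting the premium |
| B v C | same | given in B only |
| A v C | changes | none in either arm |

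**Enrollment by arm (section 5.4), in percentage points.**

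| | A | B | C | A−B | B−C | A−C |
|---|---|---|---|---|---|---|
| All | 78.4 | 70.4 | 58.6 | 8.0 | 11.8 | 19.8 |
| Gulbarga | 77.9 | 76.4 | 64.1 | 1.5 | 12.3 | 13.8 |
| Mysore | 78.8 | 63.5 | 52.3 | 15.3 | 11.2 | 26.5 |

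The step at a fixed price (B−C) is larger than A−B overall and in Gulbarga, and smaller in Mysore.

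**Is B−C more than noise?** The unclustered standard error is √(0.704×0.296/2,218 + 0.586×0.414/2,218) = 0.0143, so z = 0.118/0.0143 = 8.3. The plan gives no design effect. Assuming 2, 4 or 8, z is 5.9, 4.1 or 2.9.

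**How cash alone could produce a C excess in use.** Suppose the same share u of all assigned households uses the card in B and in C. Use per enrollee is then u/0.704 in B and u/0.586 in C, a ratio of 0.704/0.586 = 1.20. C looks 20% higher at the same price, with no difference per household.

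**Hypothesis (2).** For propensity group g, let p = A−B and c = B−C. With equal B and C weights (equal targets of 2,250), the pooled gap is A − (B+C)/2 = p + c/2. Overall this is 8.0 + 5.9 = 13.9 points. The test, however, compares high with low propensity on that gap:

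(p_high − p_low) + (c_high − c_low)/2

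On the difference scale, a cash response common to both groups cancels. Enrollment by propensity is not given. District is the only split available, and serves as an illustration. The pooled gaps are 1.5 + 12.3/2 = 7.65 in Gulbarga and 15.3 + 11.2/2 = 20.9 in Mysore, a difference of 13.25. Using A−B alone the difference is 15.3 − 1.5 = 13.8. The contrast barely moves.

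**The case against.** The strongest reply is that A v C is a legitimate price contrast. Neither arm receives cash, so it measures the ordinary uncompensated response to a premium, which properly includes the income or liquidity effect of paying. That stands. A reader might infer that any C excess over A is contaminated by cash, that B equal to A would show price has no effect, or that A v B is the only valid price test. The documents support none of these. A v B measures a compensated response, B's cash also reaches non-buyers, and preferring it is a choice of definition.

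Several narrower replies also stand. Section 10.1 is framed as a re-test of a midline finding, and that finding's description openly mentions the missing cash. Changes in who enrolls are partly covered by the selection explanation, which section 10.2 tests on all assigned households; its footnote warns about enrollee-only comparisons. A plain income effect would more naturally raise use in B, so a C excess is more likely to arise through liquidity changing who enrolls, or through a per-enrollee measure. The household-size test in section 10.1 and the tests of price paid by others in section 10.3 use neither C alone nor the B and C pool, so they are unaffected. The intent-to-treat model in section 7.1 already has separate A, B and C coefficients.

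What these replies do not supply is a comparator for section 10.1, a B v C contrast in section 10, or a rule for which contrast supports which claim. Having the coefficients makes the repair easy but does not make the repair itself.

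**Conclusion.** The point holds for the arm-based test in section 10.1 read with section 10.4: a C excess over B, at an identical premium, could be reported as a price or sunk-cost effect although it must come through the cash. The word is could, because no comparator is named.

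For hypothesis (2) in section 7.3 the point is conditional. The pool mixes a cash-compensated with an uncompensated price change, so the level of the price response is blended. The propensity contrast is biased only if the response to cash differs by propensity.

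On size, enrollment at a fixed premium differs by 11.8 points between B and C, within an A−C gap of 19.8. A reader might infer that 60% (11.8/19.8) of any price effect, or 42% (5.9/13.9) of the pooled contrast, is spurious. The documents do not support that. These are level gaps in 2015 enrollment; no card use by arm is given, and they do not measure the propensity interaction. The working assumes equal B and C weights, arm sizes at the Table 1 shares, and the design effects shown.

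**What to change.** - In section 10.1, name the comparators. For RSBY attempts and successful use, report A v B (price with cash roughly offset), B v C (cash at a fixed price) and A v C (uncompensated price), each per assigned household and per enrollee.
- State that a C excess is attributed to price or sunk cost only if it is not confined to C v B.
- Add income/liquidity to the explanations, and assess it before the residual rule in section 10.4 applies.
- In hypothesis (2) of section 7.3, show A v B and A v C by propensity beside the pooled contrast.

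This changes plan wording only, with the same data and the arm coefficients already in equation (1). The cost is a few more contrasts, each less precise than the pool.
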